Racial differences in cardiometabolic risk and complement: Multiple differences have been demonstrated between African Americans and Caucasians in the underlying pathophysiologic features of the metabolic syndrome. First and foremost, African-American adults and adolescents have consistently been shown to have lower triglyceride levels and higher HDL levels than Caucasians.^{8,10,58} Beyond this, African-American adults have impaired endothelial function compared to Caucasian adults. Specifically, endothelin 1, a potent vasoconstrictor, is increased in African Americans adults⁵⁹ and flow mediated brachial artery vasodilation⁶⁰ is diminished. Hinderliter et al^{61,62} found higher minimum FVR following vascular occlusion in African American, young adults compared to similar aged, Caucasian subjects. Endothelial dysfunction is an early predictor of both cardiovascular disease and type 2

diabetes⁶³. African-American adults, also, have increased carotid artery intima-medial thickness⁶⁴. Adolescent African-Americans with a family history of essential hypertension have increased basal and stress-stimulated endothelin 1 levels compared to similarly-selected, Caucasian adolescents⁶⁵.

In adolescents, [name] has demonstrated decreased endothelial function and increased insulin secretion in African-American adolescents⁶⁶. The endothelial dysfunction occurred primarily in the obese adolescents with diminished post-occlusion shear stress-induced vasodilation⁶⁷. In a follow up study obese African-American adolescents were found to have increased free fatty acid levels pre and post high fat meal compared to Caucasians despite having decreased triglyceride levels¹³. As discussed above there are significant interactions between complement and fat metabolism that could account for these differences.

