Regarding complement, African-Americans have been shown to have increased C4 levels⁶⁸, differences in C4 gene copy number in relationship to lupus⁶⁹⁻⁷², and different C3 polymorphism frequencies⁷³ than Caucasians. Regarding the latter have higher C3s allele frequency compared to Caucasians (93 versus 83%).⁷³ [name] studied the relationships between complement and obesity in 189 African American (Black) and 331 Caucasian (White) adult subjects from central Ohio.^{74,75} Between race differences in C3 and C4 levels were noted with increased BMI and C4 levels and decreased C3 levels in African-Americans. In each race group, strong correlations were seen between C3 and C4 protein concentrations, C4 protein levels and gene copy number of C4, BMI and C3 concentrations, BMI and C4 concentrations, and BMI and yield of C4 protein per copy of gene. In an earlier study of Hungarian subjects, positive correlations between serum C3 levels and total cholesterol concentration and between C3 levels and triglyceride levels were seen.⁴⁴

Significance: There are three important areas of innovation in the proposed studies.

1. ***Our study will be the first to explore the relationships of C3 and C4 levels to cardiovascular risk factors in African-Americans.*** This is important follow-up to our current study of nonHispanic Caucasian adolescents (Data presented below) because of the demonstrated differences in cardiovascular disease between African-American and Caucasian adults and in cardiovascular risk in adolescents. These studies will help us determine potential mechanisms for these differences early in the course of the disease.
2. ***Our study will be the first to explore the relationship between C3 polymorphisms and traditional and non-traditional anthropometric, biochemical, and functional cardiometabolic risk factors in African American adolescents.*** No studies have been done examining the role of C3 polymorphisms on cardiometabolic risk in adult or adolescent African-Americans. Again because of the increased cardiovascular disease and risk and because of the different polymorphism frequency in African-Americans it is clearly important that this population be studied.

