White Blood Cell Count	0.002 (0.0002-0.005)	0.007 (0.003-0.012)
Neutrophil Count	0.002 (0.0002-0.003)	0.007 (0.004-0.011)
Adjusted	-0.0004 (-0.001-0.002)	0.005 (0.002-0.007)
CRP	0.003 (-0.001-0.006)	0.0005 (-0.001-0.002)
IL6	0.0004 (-0.00005-0.001)	0.001 (0.0002-0.002)
LDL	0.021 (0.0004-0.041)	-0.024 (-0.074-0.027)
Adjusted	0.013 (-0.007-0.033)	-0.040 (-0.087-0.007)
HDL	-0.012 (-0.023--0.001)	-0.027 (-0.054--0.0003)
Adjusted	0.002 (-0.007-0.012)	-0.026 (-0.048-0.004)
Triglycerides	0.054 (0.025-0.083)	0.055 (-0.020-0.1)
Adjusted	0.009(-0.027-0.046)	0.057 (-0.014-0.127)
Matsuda insulin sensitivity	-0.003 (-0.004--0.001)	-0.001 (-0.006-0.004)
Adjusted	0.0003 (-0.002-0.001)	0.086 (-0.004-0.176)
Insulin Secretion	0.001 (0.0004-0.002)	0.002 (0.001-0.004)
Adjusted	-0.0001 (-0.001 0.001)	0.002 (-0.00006-0.004)
Disposition Index	-0.0004 (-0.003-0.002)	0.005 (-0.001-0.011)
Endothelin-1	-0.0002 (-0.001-0.0003)	-0.001 (-0.002-0.0004)
PAI-1	0.002 (-0.0002-0.005)	0.0003 (-0.004-0.005)
Adjusted	-0.0004 (-0.002-0.002)	-0.001 (-0.005-0.004)

increased risk in subjects with one F allele. This will be important to explore in this proposal since HDL levels differ between African-Americans and Caucasians.

FFMI decreased as C4T ($\beta=-0.73$; CI: -1.24--0.22) and C4L ($\beta=-0.46$; CI: -0.81--0.10) copy number increased. C4S, C4A, and C4B copy number were not related to any measure of body habitus. C4T gene copy number was not related to any of the cardiovascular risk factors but relationships were found for the various C4 subtypes. Interestingly, HDL was significantly

related to all 4 subtypes and increased C4L copy number increased ($\beta=3.59$; CI: 1.19-6.00), decreased as C4S ($\beta=0.4.26$; CI: -7.50—1.02) and C4B ($\beta=-5.56$; CI: -10.3--0.87) increased and increased as C4A increased ($\beta=4.33$; CI: 1.00-7.66) (**Figure 2**). These relationships are particularly interesting in light of the relationship of C4 levels to HDL and suggest that C4 may play a role in determining HDL levels.

LDL and triglyceride levels were not associated with any of the C4 gene copy numbers. Interestingly, while increased C4L gene copy number was associated with increased HDL, it was also associated decreased insulin secretion ($\beta=-0.24$; CI: -0.44-0.05) and decreased disposition index ($\beta=-0.61$; CI: -1.14--0.08).

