Complement genotypes: C3 genetic variants including the DNA sequence polymorphisms for G102R for fast and slow allotypes, and SNPs for rs11569562 and rs2250656 that modulate C3 plasma protein levels will be typed for all study subjects. Copy-number variations for total C4, C4A, C4B, long genes and short genes of C4 will be elucidated by Southern blot analyses of genomic DNA samples digested by Pmel, Taql, PshAI/Pvull and resolved by gel electrophoresis.⁷⁴ Samples for subjects with ambiguous data will be subject to realtime quantitative PCR using five different amplicons and the results will be validated as the gene copy-numbers in each subject for total C4=C4A+C4B=long genes+short genes.⁸⁵

Cardiovascular measures, glucose and insulin: IL6, CRP, endothelin 1, fibrinogen, PAI1 glucose and insulin will be measured in the CORE laboratory. Plasma lipids will be measured in the clinical laboratory of the Wexner Medical Center.

Data analysis: **Specific Aim 1:** To determine whether there are racial differences in complement C3 and C4 levels in healthy adolescents and how they relate to cardiometabolic risk factors including triglyceride and LDL levels, inflammation, and vascular function.

Statistical methods: Complement levels from African-Americans in this proposal will be compared to those from nonHispanic whites in our current study. Eligibility criteria are identical for both studies except for race. Data will be assessed for normality using the Shapiro Wilk test ($p>0.05$ indicative of normality). Non-normal data will be log normalized if possible. Unpaired t-tests will be used to compare differences in C3 and C4 levels as well as cardiometabolic risk factor results (reactive hyperemia, augmentation index, Matsuda index, insulin secretion, lipids, inflammatory markers, and PAI-1). We anticipate age and BMI differences will be minimal but should racial differences be found analysis of covariance will be done to account for any difference found.

Robust rank order regression analysis will be used to assess relationships between C3 and C4 protein levels to body habitus, lipids, inflammation, carbohydrate metabolism, and clotting factor in each race individually and in the group as a whole. Age and sex will be included in all models. The cut-off point for outliers was 3 and 100 iterations were performed. Results are presented as 95% confidence intervals.

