Sample size: Based on data from our previous study with 100 nonHispanic white subjects and 100 African-American subjects we have power 0.8 to detect a 15% racial difference in C4 levels and 7.5% difference in C3 levels.

Interpretation: There are two major portions of this aim. The first is to determine whether there are complement levels differences between the racial groups and the second is to determine how these affect previously demonstrated racial differences in cardiovascular risk¹². The former will be easily determined by comparing complement levels in the two groups. The hypothesis that these racial differences are responsible for at least some of the cardiometabolic racial differences will be proven if when complement levels are included in the regression equation they retain significance but the racial differences are lost. Lastly, even if racial differences in complement are not found or do not account for cardiometabolic risk differences it will still be important for us to determine whether the significant effects of complement described above in nonHispanic whites are present in African-American adolescents.

Specific Aim 2: To determine whether specific C3 polymorphisms, F versus S, A>G at rs11569562 and/or rs2250656, are associated with increased cardiometabolic risk in African-Americans.

Statistical Methods: As indicated above, the C3F gene has been associated with increased risk of myocardial infarction in several populations³⁶⁻³⁸ and Phillips et al⁴⁰ reported increased cardiometabolic risk in subjects with either an A/A or A/G versus subjects with a G/G genotype for both the rs11569562 and the rs2250656 sites. For rs11569562 in a European population ~ 25% of subjects had G/G and for rs2250656 ~10% had G/G. Frequencies in the African-American population are unknown. Data will be assessed for normality using the Shapiro Wilk test ($p>0.05$ indicative of normality). Non normal data will be log normalized if possible. Unpaired t-tests with unequal sample sizes will be used for comparisons for each of the measured normal variables between subjects with at least one A allele gene and those with two G alleles assuming the data is normally distributed. Mann-Whitney U tests will be used to assess non-normal data.

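### The whole-group Aim 1 regressions do not name race as a covariate, although the Aim 1 decision rule presupposes it; fitted as written, the pooled slopes mix within-race and between-race association

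*Combined protocol and SAP*

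**What the plan says.** Under Data analysis, Specific Aim 1, Statistical methods, the plan states: "Robust rank order regression analysis will be used to assess relationships between C3 and C4 protein levels to body habitus, lipids, inflammation", with carbohydrate metabolism and clotting also listed. These models are to be fitted "in each race individually and in the group as a whole. Age and sex will be included in all models". No race term and no race-by-complement term is named for the whole-group fit. The analysis of covariance in the same section deals with age and BMI imbalance in the two-group comparisons, not with these regressions.

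The Interpretation paragraph for Aim 1 treats the hypothesis as shown "if when complement levels are included in the regression equation they retain significance but the racial differences are lost". That rule needs race and complement together in one combined-group equation, which the methods do not write down.

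The background section on racial differences says that African-American adults and adolescents "have consistently been shown to have lower triglyceride levels and higher HDL levels than Caucasians". For an adult sample from central Ohio it reports "increased BMI and C4 levels and decreased C3 levels in African-Americans".

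**The concern.** Race is expected to be related to both sides of the regression. If the adult complement pattern carries over to adolescents, C3 and triglycerides are both lower in African-Americans, and C4 and HDL are both higher. A pooled model without race adds that between-race covariance to the slope. It pushes the C3-triglyceride slope upward. It also pushes the C4-HDL slope upward, against the negative slope seen in white adolescents in Table 1.

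The second half of Aim 1 asks how complement relates to risk factors. The whole-group fit uses all 200 subjects, so it has the most precision and is likely to draw attention. If it is fitted literally as the methods paragraph reads, it could suggest an association that is absent within each race, or weaken one that is present in both.

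**Working it through.** **Inputs from the documents.** Group sizes and power come from the Aim 1 sample-size paragraph: "with 100 nonHispanic white subjects and 100 African-American subjects we have power 0.8 to detect a 15% racial difference in C4 levels" and a "7.5% difference in C3 levels". The C4-HDL coefficient is from Table 1: −0.027, interval −0.054 to −0.0003, n = 75 white adolescents, adjusted for age and sex.

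**Assumptions.** The documents give no SD for complement and no size for the lipid gaps, only directions. The race gaps below (dx for complement, dy for the risk factor, in within-race SDs) are therefore assumed and shown as a range. Two-sided alpha of 0.05 is assumed for Aim 1. Fisher z and least squares stand in for robust rank regression.

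**1. The plan's own figure.** The detectable standardised difference with 100 per group is d = (1.960 + 0.842) × √(1/100 + 1/100) = 0.396. The stated 15% and 7.5% differences then imply coefficients of variation of 0.15/0.396 = 37.9% for C4 and 0.075/0.396 = 18.9% for C3. Without SDs these can be neither confirmed nor refuted. The calculation shows only that 0.4 SD is about the gap the study is powered to detect; it is not an expected gap.

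**2. Pooled correlation without race, equal groups.**

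r_pooled = (r_w + dx·dy/4) / √[(1 + dx²/4)(1 + dy²/4)]

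With r_w = 0, dx = 0.4 and dy = 0.5: 0.05 / √(1.04 × 1.0625) = 0.048. The rejection rate uses a normal mean of atanh(r_pooled) × √195, where 195 = 200 − 3 − 2 for age and sex.

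| Complement gap / risk-factor gap (SD) | Pooled r when r_w = 0 | False-positive rate |
|---|---|---|
| 0.2 / 0.2 | 0.010 | 5.2% |
| 0.4 / 0.4 | 0.038 | 8.4% |
| 0.4 / 0.5 | 0.048 | 10.2% |
| 0.4 / 0.8 | 0.073 | 17.5% |
| 0.8 / 0.8 | 0.138 | 49.1% |

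A least-squares simulation (4,000 runs, age and sex in the model) gave 7.5%, 16.9% and 48.8% at 0.396/0.396, 0.396/0.8 and 0.8/0.8. With race added, the rates were 4.6%, 4.8% and 5.0%.

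**3. A true negative slope: C4 and HDL.** From Table 1, the standard error is (0.054 − 0.0003)/(2 × 1.994) = 0.0135, so |t| = 0.027/0.0135 = 2.0 on 71 df. The partial r is −2.0/√(2.0² + 71) = −0.23. If the same r held in both races:

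- dx = 0.4, dy = 0.5: (−0.23 + 0.05)/√(1.04 × 1.0625) = −0.171
- dx = 0.4, dy = 0.8: (−0.23 + 0.08)/√(1.04 × 1.16) = −0.137

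Pooled power would be 67.5% and 48.4%, against about 90% undiluted.

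**4. A strong slope: C3 and triglycerides.** Table 1 gives 0.054 (0.025 to 0.083). The same steps give t = 3.71 and r = 0.40. The gaps in step 3 move the pooled r only to 0.43 and 0.44, so the conclusion would not change.

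**The case against.** The strongest reply is that race is unlisted rather than excluded. Age and sex are stated for all models, which sets a minimum shared by stratified and pooled fits, and race could not sit in a list that also covers race-specific models. The Interpretation paragraph needs an equation with race in it, so a reader may suppose the whole-group regression carries race. This stands: a reader might infer that the plan deliberately leaves race out, and the text does not support that. What remains is that the methods never say so. An analyst following that paragraph alone would fit age and sex only.

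Second, the race-specific regressions are planned for the same outcomes and contain no between-race covariance. This also stands. They would expose a pooled association that appears in neither race, and they answer whether the effects seen in white adolescents are present in African-Americans. A reader might infer that Aim 1 as a whole would be answered wrongly; the problem is confined to the whole-group estimates.

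Third, the size rests on gaps the documents do not give, and the complement directions come from adults. At 0.2 to 0.4 SD the distortion is small. The induced r of 0.05 to 0.07 in the middle scenarios is well below the 0.28 that the Aim 3 sample-size paragraph treats as mechanistically important. The C4-HDL example starts from an interval that barely excludes zero, in one race. These limits are accepted. They bear on the size of the bias, not on the case for specifying the model.

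**Conclusion.** The point holds as a specification gap with a real but bounded consequence. The methods name only age and sex for the whole-group regressions, while the interpretation rule presupposes race. Fitted as written, the whole-group slopes would mix two sources of association whenever the races differ on both complement and the risk factor, as the background leads one to expect for lipids.

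The distortion is negligible if both gaps are about 0.2 SD, modest near the 0.4 SD the study is powered to detect, and serious only if both are large. A weak negative C4-HDL association (r about −0.23, assumed equal in both races) would shrink to about −0.17 to −0.14 at a C4 gap of 0.4 SD and an HDL gap of 0.5 to 0.8 SD. The C3-triglyceride association would barely move. A reader might take the loss of power from about 90% to 48% as established. It is not: it depends on assumed gaps, an imprecise starting value and a stand-in for the rank method.

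**What to change.** State in the Aim 1 methods that race is a covariate, alongside age and sex, in every whole-group regression, and that the race-adjusted slope is reported as the whole-group result. Write out the equation behind the Aim 1 decision rule so that the methods and interpretation paragraphs agree. A race-by-complement term, to test whether slopes differ between races, is an optional addition, since race-specific slopes will be reported anyway.

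The cost is a sentence or two of text and one degree of freedom, plus one more if the interaction is fitted. Race is already recorded, and no further subjects, visits or assays are needed. This is a free improvement.

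### The Aim 1 regressions in the combined sample do not name race as a covariate, so their complement slopes can mix between-race with within-race differences

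*Combined protocol and SAP*

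**What the plan says.** The regression paragraph under Data analysis, Specific Aim 1, Statistical methods, plans robust rank order regressions of C3 and C4 against body habitus, lipids, inflammation, carbohydrate metabolism and clotting, "in each race individually and in the group as a whole. Age and sex will be included in all models". No other covariate is named. The covariance adjustment mentioned just before it deals with age or BMI imbalance in the comparison between races and does not put race into these regressions.

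The Background section on racial differences says: "African-American adults and adolescents have consistently been shown to have lower triglyceride levels and higher HDL levels than Caucasians". Of an adult sample from central Ohio it says: "Between race differences in C3 and C4 levels were noted with increased BMI and C4 levels and decreased C3 levels in African-Americans".

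The Aim 1 Interpretation calls the mediation hypothesis proven if, "when complement levels are included in the regression equation they retain significance but the racial differences are lost". That needs an equation holding both race and complement, but the Statistical methods never write one out. The planned comparison uses "100 nonHispanic white subjects and 100 African-American subjects".

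**The concern.** Aim 1 asks how complement relates to risk among adolescents. In a mixture of two races, a slope adjusted only for age and sex answers that question only if complement or the risk factor has the same distribution in both races. The protocol's own background suggests that neither does.

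The signs follow directly. With C3 and triglycerides both lower in African-Americans, the race contrast alone gives a positive C3-triglyceride slope. With C3 lower and HDL higher, it gives a negative C3-HDL slope. Both match the unadjusted slopes in Table 1 of the Preliminary Studies, so a spurious contribution would look like replication. With C4 and HDL both higher, the contrast is positive and works against the negative C4-HDL slope in Table 1.

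The combined fits have the largest sample in Aim 1, so they are likely to be read as the most precise estimates. The Subjects section limits new recruitment to African-Americans to avoid racial confounding. Combining them with the white cohort without a race term can bring it back.

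**Working it through.** **Inputs from the documents**
- Planned groups: 100 + 100. The preliminary white sample had 75.
- Aim 1 power statement: "we have power 0.8 to detect a 15% racial difference in C4 levels and 7.5% difference in C3 levels".
- C4-HDL slope in whites (Table 1): -0.027, 95% CI -0.054 to -0.0003.
- HDL SD about 13 (12.2 and 13.1 in the two C3 allele groups).

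**Assumptions.** Two-sided alpha 0.05; equal within-race SDs; the same within-race slope in both races; race gaps over a range, because the documents give directions but no sizes.

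**1. The plan's own figure.** Aim 1 gives no mean or SD, so its power statement cannot be reproduced. It can only be solved backwards. The detectable standardised difference is (1.960 + 0.842) × √(2/100) = 0.396 SD. The percentages then imply coefficients of variation of 15/0.396 = 37.9% (C4) and 7.5/0.396 = 18.9% (C3). So 0.40 SD is the gap the plan can detect, not one it predicts. It serves here as the middle of a range.

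**2. Within-race C4-HDL correlation.** SE = (0.054 - 0.0003)/(2 × 1.96) = 0.0137. t = -0.027/0.0137 = -1.97. With 71 df, r = -1.97/√(1.97² + 71) = -0.23.

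**3. Slope without race.** Let dx and dy be the race gaps in complement and risk factor, in within-race SDs, and r the within-race correlation. With equal groups:
- slope = (r + dx·dy/4)/(1 + dx²/4)
- correlation = (r + dx·dy/4)/√[(1 + dx²/4)(1 + dy²/4)]

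Example, dx = 0.4 and dy = 0.5 (an HDL gap of about 0.5 × 13 = 6.5):
- True r = 0: correlation = 0.05/√(1.04 × 1.0625) = 0.048. By Fisher z with N = 200, 0.048 × √197 = 0.67, which rejects about 10% of the time.
- True r = -0.23: slope = (-0.23 + 0.05)/1.04 = -0.173, or 75% of the true value. The correlation is -0.171, z = 0.173 × √197 = 2.43, and power is 0.68. With race in the model it is 0.91.

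**4. Rank-based simulation.** Ranks of the risk factor were regressed on ranks of complement with age and sex, with and without race. This stands in for the planned robust rank regression. Risk-factor gap 0.5 SD, 100 + 100:

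| Complement gap | False positives, no race | Power at r = -0.23, no race | With race |
|---|---|---|---|
| 0.2 SD | about 6% | about 0.77 | about 5%; 0.87 |
| 0.4 SD | 9-10% | about 0.63 | about 5%; 0.87 |
| 0.6 SD | about 17% | about 0.47 | about 5%; 0.87 |

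At a 0.4 SD complement gap, risk-factor gaps of 0.3 and 0.8 SD give false positives of about 6% and 18%, and power of about 0.73 and 0.43. With 75 + 100 subjects and gaps of 0.4 and 0.5 SD, power is 0.57 without race and about 0.82 with it.

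**5. Full cancellation.** The C4-HDL slope reaches zero only when dx·dy = 4 × 0.23 = 0.92, about 0.96 SD in both variables.

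**The case against.** The strongest reply is that the same sentence plans fits within each race, which race gaps cannot distort. With r = -0.23 in each race and 100 per group, at least one of the two is significant in about 82% of studies (uncorrected; about 10% under the null). A combined slope found in neither race would be visible beside them. This stands, and it limits the damage. It does not correct the combined estimate or its interval, which remain planned outputs, and the plan does not say which result to believe if they disagree.

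A second reply is that naming age and sex sets a minimum, and that the Interpretation rule presupposes race in the equation. That is fair as far as it goes. But that rule asks whether race effects disappear once complement is added, its model is not written out, and it does not alter the covariates stated for the association models.

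A third reply is that the gaps may be small. The complement directions quoted above come from adults whose BMI also differed by race, whereas the plan expects BMI differences here to be minimal. At a 0.2 SD complement gap the harm is small: false positives of 6-8%, and power of 0.64-0.82 over risk-factor gaps of 0.3 to 0.8 SD.

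A reader might infer that the combined models will create false associations and hide the C4-HDL one. The documents do not support that. They give no gap sizes, middling assumed gaps weaken the slope rather than hide it, and the race-specific fits would show the discrepancy. Nor do they show that the C4-HDL association exists in both races; the estimate comes from 75 white adolescents, with an interval ending just below zero. A similar argument about C4 and endothelial function falls outside this point, because vascular function is not in the list of regressions, although the Aim names it.

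**Conclusion.** The concern holds in a conditional form. As written, the combined-sample regressions are open to confounding by race, and the protocol's background gives reason to expect it for the lipid outcomes. C3-triglyceride and C3-HDL slopes can be inflated, and a negative C4-HDL slope can be weakened.

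The harm runs from slight at a 0.2 SD complement gap to material at 0.6 SD, where at a 0.5 SD risk-factor gap the error rate is roughly three times nominal and power is nearly halved. These figures rest on assumed gaps, a common within-race slope, and a simple rank regression standing in for the robust procedure. The direction of the bias depends only on the signs stated in the background. The race-specific analyses are sound in this respect.

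**What to change.** In Specific Aim 1, Statistical methods, change the covariate sentence to: *Age and sex will be included in all models, and race in all models fitted to the group as a whole.* Report the race-adjusted slope as the combined-sample association, next to the race-specific slopes already planned. These also show whether a common slope is reasonable. If a slope without race is shown, label it as mixing within-race and between-race differences.

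The cost is one sentence and one degree of freedom in a model with about 175 to 200 subjects. No new data are needed.
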